7.3 Clinical Laboratory Assessments

Hematology, Coagulation, Blood Chemistry and Urinalysis data will be summarized by treatment group and visit. All clinical laboratory data will be converted to International System of Units (SI). Both raw and change from baseline values will be summarized by presenting the descriptive statistics by treatment group and visit.

Central and local drug and alcohol test results and pregnancy tests results will be listed.

7.4 Vital Signs

Vital signs raw and change from baseline values will be summarized by presenting the descriptive statistics of blood pressure, heart rate, temperature, and respiratory rate measurements by treatment group and visit.

7.5 ECG

The ECG measurements (PR Interval, Heart Rate, QRS Interval, QT Interval [uncorrected], and QTcF [Friderica's QT Correction Formula]) will be summarized by presenting descriptive statistics of raw data and change from baseline values by treatment group and visit.

7.6 Physical Examination

A listing of physical examination abnormalities will be provided.

8. DATA SAFETY MONITORING BOARD

An independent Data Safety Monitoring Board (DSMB) will monitor the trial. The DSMB will comprise of medical professionals with expertise in NASH and clinical trials and are external to the Sponsor. The DSMB will meet periodically or as needed to review accumulating safety data and any available PK data collected throughout the trial. See the DSMB Charter for details.

9. INTERIM ANALYSIS

[REDACTED]

10. SAMPLE SIZE AND POWER CALCULATIONS

[REDACTED]

12.2 Appendix B: List of Proposed Tables

Summary of Subject Disposition – All Subjects

Summary of Protocol Deviations – Safety Set

Summary of Demographics – Safety Set

Summary of Medical History by System Organ Class and Preferred Term – Safety Set

Summary of Prior and Concomitant Medications – Safety Set

Summary of Non-drug Therapies by System Organ Class and Preferred Term – Safety Set

Summary of Biomarkers: Change from Baseline – Safety Set

Summary of Biomarkers: Percent Change from Baseline – Safety Set

Summary of Exposure – Safety Set

Overall Summary of Treatment-emergent Adverse Events – Safety Set

Treatment-emergent Adverse Events by System Organ Class and Preferred Term – Safety Set

Treatment-emergent Adverse Events by System Organ Class, Preferred Term and Highest Severity – Safety Set

Treatment-emergent Adverse Events by System Organ Class, Preferred Term and Strongest Relationship to Study Drug – Safety Set

Treatment-emergent Serious Adverse Events by System Organ Class and Preferred Term – Safety Set

Treatment-emergent Adverse Events Leading to Study Withdrawal by System Organ Class and Preferred Term – Safety Set

Summary of Blood Chemistry Results – Safety Set

Summary of Hematology Results – Safety Set

Summary of Urinalysis Results – Safety Set

Summary of Vital Signs – Safety Set

Summary of ECG – Safety Set

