- CRV431, 75 mg, softgel capsule, orally QD, in fasted condition
- Placebo, softgel capsule orally QD, in fasted condition

Duration of treatment: Full treatment duration will be defined as 28 days of treatment with CRV431 or placebo.

Criteria for evaluation:

Safety:

Safety and tolerability parameters, including adverse events (AEs), serious adverse events (SAEs), AEs of special interest, physical examinations including weight and height, concomitant medications, laboratory assessments including blood chemistry, hematology and coagulation, urinalysis, pregnancy screening, clinical safety laboratory parameters, ECG, and vital sign assessments, will be determined.

Pharmacokinetics:

Whole blood PK samples will be analyzed for the concentrations of CRV431 along with its major metabolites using a validated liquid chromatography/tandem mass spectroscopy (LC-MS/MS) assay. Subjects will have whole blood PK samples collected at the following time points on Days 1 and 28: 0 hour (pre-dose), 2.0, 4.0 and 8.0 hours (post-dose). A single sample of whole blood will be collected for PK on Day 14 (pre-dose). Standard non-compartmental PK parameters will be calculated from whole blood.

[REDACTED]

[figure not shown]
[REDACTED]	[REDACTED]	[REDACTED]
[REDACTED]	[REDACTED]	[REDACTED]
[REDACTED]	[REDACTED]	[REDACTED]
[REDACTED]	[REDACTED]	[REDACTED]
[REDACTED]	[REDACTED]	[REDACTED]

[REDACTED]

Statistical methods:

The sample size is not based on statistical considerations. It is expected that the number of subjects per cohort, 12 subjects in Cohort A, 6 subjects in Cohort B, 12 subjects in Cohort C and 6 subjects in Cohort D is enough to assess the safety, tolerability, and PK of CRV431, as well as providing a preliminary indication of its antifibrotic activity, based on biomarkers, for Phase 2B study planning purposes. To evaluate drug effect and dose response, comparisons of Cohorts will include Cohort A versus Cohort B, Cohort C versus Cohort D and Cohort A versus Cohort C.

Data will be listed by subject and summarized using descriptive statistics.

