12.3.2. Analysis of Covariance

Placebo subjects will be used for comparison with all presumed NASH treatment subjects using the following analysis.

An analysis of covariance (ANCOVA) will be performed on the ln-transformed AUC_{0-inf} and C_{max} . The ANCOVA model will contain a categorical factor of population (for subjects with F2/F3 presumed NASH, and F2/F3 presumed NASH placebo subjects), a categorical covariate (sex), and continuous covariates (age, weight, BMI and ideal body weight).

The comparisons of interests are:

- CRV431-treated F2 presumed NASH subjects versus placebo treated F2 presumed NASH subjects stratified by dosing cohort, i.e. Cohort A (75 mg QD) versus Cohort C (225 mg QD);
- CRV431-treated F3 presumed NASH subjects versus placebo treated F3 presumed NASH subjects stratified by dosing cohort, i.e. Cohort A (75 mg QD) versus Cohort C (225 mg QD);
- CRV431-treated pooled F2/F3 presumed NASH subjects versus pooled placebo treated F2/F3 presumed NASH subjects stratified by dosing cohort will only be evaluated for differences [REDACTED]

A full covariate population PK/PD model will be developed for exploratory purposes.

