2.1.2 Secondary Objectives

- To evaluate non-invasively the antifibrotic activity of a QD dose of CRV431, as measured by quantification of selected biomarkers of fibrosis, in presumed NASH F2/F3 subjects over 28 days of dosing.

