4. GENERAL CONSIDERATIONS FOR DATA ANALYSIS

Unless otherwise specified, continuous variables will be summarized by presenting the number of non-missing observations, mean, standard deviation, median, minimum, and maximum. Categorical variables will be summarized by presenting the number of subjects and percentages for each category.

All mean and median values will be formatted to one more decimal place than the measured value. Standard deviation values will be formatted to two more decimal places than the measured value. Minimum and maximum will be formatted to the same number of decimal places as the measured value.

Analyses will be performed using SAS for Windows statistical software, version 9.4 or higher (SAS, Cary, NC), except where other software may be deemed more appropriate.

[REDACTED]

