4.6 Data Derivations and Transformations

Baseline is defined as the last non-missing value prior to the first dose of CRV431 or placebo administration.

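### The readable biomarker outputs are raw and arithmetic percent change without baseline adjustment; a baseline-adjusted log-scale comparison would be a better summary at almost no cost (minor)

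*Combined protocol and SAP*

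**What the plan says.** Fibrosis biomarkers carry the secondary objective (SAP 2.1.2): "To evaluate non-invasively the antifibrotic activity of a QD dose of CRV431, as measured by quantification of selected biomarkers of fibrosis". The synopsis wants a preliminary indication of antifibrotic activity for Phase 2B planning and names three cohort comparisons: A v B, C v D and A v C. Its general statement on analysis is "Data will be listed by subject and summarized using descriptive statistics".

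The biomarker outputs that can be read are two entries in SAP Appendix B: "Summary of Biomarkers: Change from Baseline" and "Summary of Biomarkers: Percent Change from Baseline", both on the Safety Set. SAP section 4 gives the default content of such tables: "continuous variables will be summarized by presenting the number of non-missing observations, mean, standard deviation, median, minimum, and maximum". SAP 4.6 fixes the reference value: "Baseline is defined as the last non-missing value prior to the first dose of CRV431 or placebo administration".

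Other readable text bears on the point:
- Protocol 12.3.2 has an ANCOVA, but its readable outcomes are drug exposure (ln AUC0-inf and ln Cmax).
- Protocol 6.4.2 and SAP 2.2.1.2 plan exploratory PK/PD modelling of all biomarkers.
- SAP 6.1 states that there are no efficacy endpoints.

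SAP 6.3, the opening of protocol 12.3, the end of SAP section 4 and the end of the pooled-comparison bullet in protocol 12.3.2 are redacted.

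**The concern.** The plan promises cohort comparisons on biomarkers, but the readable outputs give no between-arm estimate, no confidence interval, no log-scale summary and no adjustment for the baseline value.

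Two properties of those outputs matter. First, a ratio of two positive, right-skewed measurements has an arithmetic mean above 1 even when nothing has changed, so mean percent change drifts upward and is pulled by subjects with low baselines. Second, in arms of 12 and 6 a chance baseline imbalance passes partly into an unadjusted change.

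These numbers are meant to feed Phase 2B planning. At stake are a misread within-arm mean and an effect size estimated less precisely than the data allow.

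**Working it through.** **Inputs.** From the documents: 12 active and 6 placebo at each dose level (protocol 7.2); the two tables and their statistics as above; Pro-C3 >15.5 ng/mL named as an entry criterion (protocol 5.3); re-screening of subjects who failed only ELF or only Pro-C3 (protocol 8.2); ELF scheduled at Screening and Day 28 (protocol Table 3). The documents give no biomarker SD, CV or baseline-to-Day-28 correlation r. These are assumed below, with log-normal markers. The plan states no figure for this analysis, so there is none to reproduce; the sample size is expressly not based on statistical considerations.

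**1. Mean percent change when nothing changes.** If a subject's log ratio has mean 0 and SD s, the expected percent change is exp(s²/2) − 1.
- s = 0.3: exp(0.045) − 1 = +4.6%
- s = 0.5: exp(0.125) − 1 = +13.3%
- At log SD 0.4 and r = 0.7, the settings of step 5: s² = 2 × 0.16 × 0.3 = 0.096, giving exp(0.048) − 1 = +4.9%

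Under the same conditions and without selection on baseline, the median percent change is 0 and the mean raw change is 0.

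**2. Between arms.** The artefact is the same in both arms. In 40,000 simulated 12 v 6 trials with no effect (CV 50%, r = 0.5), the mean percent change was +11.8% on active and +11.8% on placebo, a difference of about 0.

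**3. Selection on the same marker.** If the qualifying value also serves as baseline, regression to the mean pulls follow-up values down. With no drug effect, CV 50% and r = 0.7 (1,000,000 simulated subjects):

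| Entry cut-off on baseline | Mean % change | Raw change, % of mean baseline | Geometric mean % change |
|---|---|---|---|
| none | +7.0 | 0 | 0 |
| 25th percentile | +0.3 | −3.6 | −5.8 |
| median | −5.1 | −7.6 | −10.6 |
| 75th percentile | −11.4 | −12.9 | −16.5 |

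The direction of a within-arm mean under no effect is therefore unknown for Pro-C3 and ELF. The geometric mean removes the ratio artefact but not regression to the mean.

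**4. Baseline imbalance and precision.** The SE of the baseline difference at 12 v 6 is √(1/12 + 1/6) = 0.50 SD. A one-SE imbalance shifts the unadjusted change contrast by (1 − r) × 0.5 SD: 0.25 SD at r = 0.5 and 0.05 SD at r = 0.9.

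The variance of the baseline-adjusted contrast relative to unadjusted log change is (1 + r)/2, times about 1 + 1/14 for estimating the slope with 18 subjects:
- r = 0.5: 0.75 × 1.071 = 0.80
- r = 0.7: 0.85 × 1.071 = 0.91
- r = 0.8: 0.90 × 1.071 = 0.96
- r = 0.9: 0.95 × 1.071 = 1.02

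**5. Power for a 30% fall, 12 v 6.** Simulated with log SD 0.4 and two-sided 5% tests, using pooled-variance t tests for the two change measures. Rejection under no effect stayed near 5%.

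| r | Raw change | Percent change | Log ANCOVA with baseline |
|---|---|---|---|
| 0.5 | 32% | 41% | 46% |
| 0.7 | 46% | 60% | 62% |
| 0.8 | 61% | 77% | 77% |
| 0.9 | not tabulated | 97% | 96% |

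The gain over raw change is clear at r = 0.5 to 0.8. Over percent change it is 5 points at r = 0.5, 2 points at 0.7, and nothing at 0.8 to 0.9.

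**The case against.** The strongest reply is that the places where a biomarker model would stand are blacked out. Nor can Appendix B be read as a complete list: it is headed as proposed tables and contains no PK table, although PK is a primary objective and protocol 12.3.2 and 12.3.3 specify an ANCOVA with ratios and 90% CIs. This stands. A reader might infer that biomarkers will be analysed only by change and percent change; the documents do not support that inference.

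A reader might also fault the ANCOVA in protocol 12.3.2 because its covariate list, "a categorical covariate (sex), and continuous covariates (age, weight, BMI and ideal body weight", has no baseline outcome value. That does not follow. The readable text applies that model to drug exposure, which is no guide to how biomarkers are modelled.

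A third tempting reading is that the tables as a whole would show a spurious increase. Only the arithmetic mean percent change within an arm has that property. The planned median and the raw change do not, the null active-placebo difference does not, and selection at entry may reverse the sign. Nor is baseline ignored: both measures use it, as subtrahend or divisor, without adjusting for it.

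Finally, the biomarker analysis is descriptive and the sample size has no statistical basis, so power at 5% is not the plan's decision criterion. This also stands and limits the severity. It does not remove the case for a usable effect estimate, since the synopsis wants these data for Phase 2B planning.

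**Conclusion.** The point holds for the readable outputs, as a minor improvement. A within-arm arithmetic mean percent change should not be read as drug effect: the ratio artefact is +4.6% to +13.3% for a log-ratio SD of 0.3 to 0.5, and regression to the mean may cancel or outweigh it for markers used at entry. The randomised active-placebo contrast within a dose level is not biased under no effect; what it can lose is precision. That loss is material for raw change (about 46% v 62% power at r = 0.7), small for percent change (60% v 62%), and absent relative to percent change at r = 0.8 to 0.9.

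All these sizes rest on assumed log-normal markers, SDs, correlations, cut-off percentiles and a 30% effect. Whether the redacted text already contains an adjusted model cannot be judged from the public documents.

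**What to change.** Unless the redacted sections already do this:
- For concentration biomarkers, compare cohorts by ANCOVA on ln(Day 28) with treatment group and ln(baseline), and report geometric mean ratios with confidence intervals.
- For ELF, if the score is already on a log-type scale, fit the same model to the score itself with its baseline.
- In the percent-change table, show the geometric instead of the arithmetic mean percent change, with a note that within-arm values are not estimates of drug effect.

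The cost is SAP text, one model per biomarker and one degree of freedom. At 12 v 6 that is a slight loss if r is as high as 0.9 (variance ratio about 1.02). No new data are needed.
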